12.2	Methods to Minimize Risks.....	25
12.3	Emergency Procedures	26
12.4	Unblinding Procedures in Case of Emergency	26
13	Ethical Considerations.....	26
13.1	Good Clinical Practice.....	26

13.2 Institutional Review Board (IRB) Review and Informed Consent.....26

13.3 Confidentiality.....26

13.4 Declaration of Interests.....27

13.5 Publication Policy.....27

Abbreviations

AA	Amino Acid
AE	Adverse Event
ABI	Ankle Brachial Index
ABPM	Ambulatory Blood Pressure Monitoring
AHA	American Heart Association
ANP	A-type Natriuretic Peptide
ATP	Adenosine Triphosphate
BNP	B-type Natriuretic Peptide
CARDIA	Coronary Artery Risk Development in Young Adults
cGMP	Cyclic Guanosine Monophosphate
CGM	Continuous Glucose Monitoring
CKD	Chronic Kidney Disease
CNP	C-type Natriuretic Peptide
CRF	Case Report Forms
CT	Computed Tomography
CTSI	Clinical and Translational Science Institute
DNP	Dendroaspis Natriuretic Peptide
DSMB	Data Safety Monitoring Board
ECG	Electrocardiogram
EF	Effect Size
fMRI	Functional Magnetic Resonance Imaging
GRE-EPI	Gradient Recall Echo Planar [MRI]
GXT	Graded Exercise Test
HIPAA	Health Insurance Portability and Accountability Act
HF	Heart Failure
IC	Intermittent Claudication
ICMJE	International Committee Of Medical Journal Editors
IDS	Investigative Drug Pharmacy
IRB	Institutional Review Board
MCRU	Masonic Clinical Research Unit
MEBRL	Molecular Epidemiology and Biomarker Research Laboratory
MG	Medial Gastrocnemius
MRI	Magnetic Resonance Imaging
MRS	Magnetic Resonance Spectroscopy
MWD	Maximal Walking Distance
NPs	Natriuretic Peptides
NPR	Natriuretic Peptide Receptor

NT-proBNP	N-terminal pro B-type natriuretic peptide
PAD	Peripheral Artery Disease
PAD-QOL	Quality of Life
PCr	Phosphocreatine
PFW	Pain Free Walking Distance
PHI	Protected Health Information
PI	Principal Investigator
PKG	Protein Kinase G
Pro-BNP	Prohormone Brain Natriuretic Peptide
PTA	Percutaneous Transluminal Angioplasty
ROI	Region of Interest
SAE	Serious Adverse Event
SBP	Systolic Blood Pressure
SD	Standard Deviation
SF-36	36-item Short Form
SI	[MR] Signal Intensities
SNR	Signal to Noise Ratio
Sol	Soleus
SQ	Subcutaneous
TE	Echo Time
UPIRTSO	Unanticipated Problems Involving Risk to Subjects or Others
WIQ	Walking Impairment Questionnaire

1 Introduction

1.1 Background and Significance

Peripheral arterial disease (PAD) affects about 12 million individuals in the United States^{1,2}. The functional physical limitations observed in patients with PAD progressively deteriorate from a reduction in mobility to a complete loss of independence³. Unfortunately, the available therapeutic options are limited in success rate, adherence and long-term benefits⁴. Functional physical limitations observed in patients with PAD are associated with impaired mitochondrial and microvascular function⁵⁻⁷. Because natriuretic peptides have been shown to improve oxygen consumption and blood flow in skeletal muscles^{8,9}, we propose that increasing the levels of natriuretic peptide (NPs) using sacubitril/valsartan [LCZ696 (Entresto), Novartis Pharmaceuticals Corp.] initially designed to treat patients with heart failure¹⁰, could be used as novel therapeutic option. These are the two most important biological mechanisms implicated in the functional limitations observed in PAD and could provide significant functional beneficial effects to this type of patient.

The mitochondrial and renal effects of NP's are exerted predominantly through activation of NP receptors A (NPR-A), while the endothelial, vascular and anti-fibrotic effects are related to activation of NPR-B¹¹. Atrial natriuretic peptide (ANP) and B-type natriuretic peptide (BNP) act through activation of NPR-A and C-type natriuretic peptide (CNP) activates NPR-C¹². Because sacubitril inhibits the enzyme that breakdown ANP, BNP as well as CNP, then the activity levels of all NPs should be increased. Therefore, the potential effects of sacubitril should include mitochondrial genesis, promotion of vascular growth, improvement of endothelial function and anti-fibrotic effects.

1.1.1 Peripheral Arterial Disease (PAD) pathophysiological mechanisms

PAD is caused by a decrease in oxygen delivery and utilization that is unable to meet the metabolic demands of active skeletal muscles. Obstruction of large arteries by atherosclerotic plaques prevents adequate delivery of oxygen⁵ and the resulting dysfunctional microvasculature^{7,8} is unable to distribute blood to those active muscle fibers. Mitochondrial dysfunction, independent of oxygen delivery, cannot regenerate ATP and PCr to satisfy the metabolic demands of those active skeletal muscle fibers⁵. In addition, a decrease in arterial elasticity due to atherosclerosis also impairs blood flow in patients with PAD¹³. Therefore, treatment for patients with PAD should be designed to target the mechanisms that impair oxygen delivery, utilization and decrease arterial stiffness.

1.1.2 Treatment options for patients with PAD

The low success rate of the drugs that are used in the treatment of PAD is probably related to the fact that none of them directly targets the mechanisms implicated in PAD¹⁴. Surgical revascularization with percutaneous transluminal angioplasty (PTA) or with stents leads to significant improvements in blood flow, maximal walking distance (MWD) and pain free walking distance (PFWD)^{15,16}. However, despite the initial high success rate¹⁵, restenosis occurs in 63% and 37% of cases within the first year following primarily successful PTA or stent, respectively¹⁵. Another option, therapeutic angiogenesis, is still in the experimental phase and has not had the expected success in humans¹⁷. Exercise

rehabilitation programs are more successful than PTA in maintaining MWD and PFW, as long as patients continue to exercise¹⁸. Unfortunately, patients with pain at rest are unable to participate in exercise rehabilitation programs and 2 years patient are only of 36% and 68% in center and home based programs, respectively¹⁹.

1.1.3 Natriuretic peptides: a potential treatment option

The benefits in functional clinical parameters maximal walking duration (MWD) and pain free walking duration (PFW) with exercise training are related to improvements in endothelial function, and increases in capillary and mitochondrial density²⁰. These changes improve oxygen delivery and utilization and clearance of metabolic waste products. A potential treatment option that would target two of the most important pathophysiological mechanisms in PAD are NPs. ANP and BNP are synthesized in the atrium and ventricle of the heart in response to pressure and volume overload inducing natriuresis and vasodilation and regulating blood pressure²¹, CNP is synthesized by endothelial cells and renal epithelial cells²². NPs act by binding to particulate membrane bound guanylyl cyclase-coupled receptors called natriuretic peptide receptor A and B (NPR-A and B)¹¹. Once activated, they act by increasing the intracellular messenger cyclic guanosine monophosphate (cGMP), which then acts on a cGMP-dependent protein kinase (PKG) mediating specific physiological functions²². ANP and BNP, but not CNP, bind specifically to NPR-A and only CNP binds to NPR-B²² (Figure 1). ANP and BNP acting by activating NPR-A appears to be related to angiogenesis and mitochondrial genesis^{11,22} and CNP acting through NPR-B is implicated in vasodilation, angiogenesis and anti-fibrotic activity^{10,11}. The activation of NPR-A is most likely responsible for the increased perfusion of tissues, for increasing muscle oxygen consumption and improvements in insulin sensitivity observed in transgenic mice that overexpressed BNP or were infused with Carperitide, a homolog of ANP^{8,23}. Activating NPR-B would induce vasodilation, increase angiogenesis and may decrease fibrosis in the peripheral vasculature, which would improve arterial elasticity.

1.1.4 Entresto (sacubitril/valsartan) biochemical characteristics and physiological properties

Sacubitril is a molecule that inactivates neprilysin, a neutral endopeptidase responsible for degrading natriuretic peptides (Figure 1). The combination sacubitril/valsartan given to patients with heart failure raises serum and urinary levels of cGMP, a marker of NPs activity, by 35% and 25%, respectively²⁴, due potentially to an increase in ANP, BNP and CNP (Figure 1).

Sacubitril was proposed as a treatment option for patients with heart failure due to the diuretic and vasodilatory effects of natriuretic peptides. Sacubitril cannot be given alone as it raises the levels of angiotensin II and for this reason is combined with valsartan, an angiotensin II receptor blocker. This combination, sacubitril/valsartan, has been shown to decrease mortality for patients with heart failure²⁵ and it is currently approved by the FDA and it is being used for that purpose²⁶. In addition, a similar compound, Omapatrilat, which inhibits both neprilysin and angiotensin converting enzyme (ACE) has been shown to prevent endothelial cell permeability and atheroma formation in a rabbit model of atherosclerosis²⁷. The effects of natriuretic peptides on microvascular and mitochondrial function

have not been studied in human skeletal muscle. This study would provide us with the supporting evidence to determine if raising natriuretic peptides improves microvascular and mitochondrial function and if this is positively associated with exercise tolerance. Having a therapeutic option to improve microvascular and mitochondrial function would be clinically important because it could lead to effective therapeutic strategies for patients with peripheral arterial disease, diabetes and in elderly subjects who have limited exercise capacity due to low perfusion and oxygen utilization in skeletal muscles.

1.1.5 Clinical trial with carperitide, what do we still need to learn?

The effects on pain free walking duration (PFWD) of 2 weeks of intravenous infusion of carperitide, a homolog of ANP, were tested in PAD patients with different degrees of severity⁸. That study showed a decrease in pain at rest, an increase in ankle/brachial blood pressure index and in PFWD with minimal side effects. However, the study only had 13 patients, PFWD was assessed in 4 patients and did not have a placebo group and the functional and structural changes in mitochondria and the microvasculature were not determined. Assessing those parameters would provide a sound biological basis for the effects of increasing the activity levels of NPs on the functional clinical limitations and for recommending Entresto for the treatment of PAD.

1.1.6 Significance

Although there are an estimated 12 million individuals in the United States with PAD, this is an underestimation because about 50% of patients with PAD are undiagnosed². Furthermore, patients with PAD have an 80% higher risk of disability than those without PAD²⁸. Among patients with PAD, there is a higher risk of disability in those with poor functional performance at baseline²⁹ and with lower ABI³⁰. In addition, those with the greatest rate of decline in mobility had a 3 fold higher rate of disability when compared to those with the lowest rate of decline³¹. The inability to be mobile and participate in exercise rehabilitation programs leads to further deterioration culminating in limb amputation, loss of independence and greater risk of mortality³¹. Furthermore, total annual costs associated with vascular-related hospitalizations in patients with PAD were estimated at 21 billion in the year 2004³², this greatly increases when the cost for rehabilitation are included³³. Entresto may be beneficial maintaining and improving mobility, which is a very important step in the prevention of disability, in lowering the risk of mortality and decreasing the costs associated with PAD.

1.2 Study Aims/Objectives

Primary Objective:

1. To assess the effects of 12 weeks of Entresto on the functional clinical parameters maximal walking duration, pain free walking duration and 6 minute walk test of patients with PAD.

Secondary Objective:

1. To assess if changes in functional clinical parameters are related to improvements in microvascular and mitochondrial function and to assess the effects of increasing NP activity on arterial elasticity.
2. To assess the time required for functional improvements (6 minute walk test) to return to baseline

values following 12 weeks of Entresto.

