Participant will undergo a baseline symptom-limited treadmill test as described below. The treadmill test will be used to determine MWD and PFWD and will be repeated at follow-up. The graded exercise test (GXT) is initiated at 2.0 mph (3.2 km/h) at 0% grade, and every 2 minutes the grade is increased by 2%³⁸. The time at which the participant first starts feeling claudication symptoms is defined as the pain free walking duration and the time at which participants has to stop walking is designated as the maximal walking duration. During the GXT, participants will rate their claudication pain severity every 30 seconds, using the following claudication pain scale: 1 = no pain, 2 = initial onset of mild claudication pain, 3 = moderate pain, 4 = submaximal and 5 = maximal claudication pain (point at which the participant will request to stop). Recent evidence suggest that the 6 minute walk test is an accurate predictor of the response to treatment, mortality rate and mobility loss in patients with PAD³⁹. Therefore, we will also perform the 6 minute walk test because it offers the possibility of an inexpensive, accurate and valid tool to assess the effects of Entresto. The 6 minute walk test will be performed in a 20 meter corridor⁴⁰. Patients will be asked to walk as quickly as they can along the corridor for 6 minutes to cover as much distance as possible. They will be allowed to stop if they have to, but will be encouraged to continue again as soon as they are able. During the time that the participant stops walking the clock will continue to run. At the end of test the distance covered is measured.

[figure not shown]

Figure 2. T_1 weighed image of the lower leg showing the distinct location of the soleus and medial gastrocnemius muscles.

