9.1 Statistical Methods

General baseline characteristics will be described using mean and proportions. Smirnov-Kolmogorov tests will be used to test normality of distribution of variables. For variables that do not follow the normal distribution, log transformation will be performed. Linear simple and multiple regressions will be performed to assess

association between the effects of Entresto on metabolic and physiological changes with clinical functional variables. Differences between the placebo and the

Entresto group will be assessed using independent sample t-test and Chi-square for quantitative and categorical variables, respectively. Change following the 12 week clinical trial in metabolic and physiological parameters will be assessed using paired sample t-test. Repeated measures analysis of covariance will also be used to evaluate differences between groups as a function of time. A p value < 0.05 will be used to determine statistical significance. Effect size (EF) calculated as $EF = (\text{mean Entresto group} - \text{mean placebo}$

group)/SD (control group) will be used to assess the clinical significance of the effects of Entresto⁶³. The PI will be in charge of performing all statistical calculations using SAS v 9.3 by SAS Institute Inc., Cary, NC. [name] Jr. Professor at the School of Public Health a statistician with more the 800 publications will be a consultant in statistical analysis of the data.

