9.2 Power analysis

Sample size for a double blind randomized clinical trial was determined using SAS version 9.3 (SAS Institute Inc., Cary, NC, USA). Sample size is based on the mean (SD) values obtain in a clinical trial that measured the effects of carperitide on pain free walking distance in patients with PAD 5. The mean (SD) pre post change in pain free walking distance was of 278 (240) m. [We have estimated that for a power 0.85 we will need 15 subjects per group to reject the null hypothesis with Type I error probability of 0.05] (Figure 6).

10 Clinical Management

[name] Assistant Professor in the Department of Medicine Division of Kidney Diseases and Hypertension will be the study physician for clinical trial. This includes adjusting the dose of Entresto (based on information obtain from the Entresto information sheet, Novartis), development of safety procedures and treatment of medical complications. The main PI ([name] MD PhD) will be the person directly in charge of admittance of patients into the study, performing and supervising the diagnostic tests and the metabolic, physiological and clinical functional testing.

11 Risks/Benefits

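### Three unranked primary walking outcomes are tested at p < 0.05 with no success rule, so the 0.05 and 0.85 in section 9.2 hold for pain-free walking alone and not for the primary objective

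*Combined protocol and SAP*

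**What the plan says.** Section 1.2 states a single primary objective: the effect of 12 weeks of treatment on "the functional clinical parameters maximal walking duration, pain free walking duration and 6 minute walk test of patients with PAD". The three outcomes stand in one list with no order among them.

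Section 9.1 describes the between-group comparison in two ways. Differences between placebo and the "Entresto group will be assessed using independent sample t-test and Chi-square for quantitative and categorical variables, respectively". Then: "Repeated measures analysis of covariance will also be used to evaluate differences between groups as a function of time". It does not say which of the two decides the primary objective, or whether the t-test is on the week-12 value or on change. The only threshold is general: "A p value < 0.05 will be used to determine statistical significance". Neither section 9.1 nor any other section gives a hierarchy, a multiplicity adjustment or a definition of trial success.

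Section 9.2 sizes the trial on one outcome. "The mean (SD) pre post change in pain free walking distance was of 278 (240) m", taken from the earlier carperitide study, leads to the statement that "for a power 0.85 we will need 15 subjects per group to reject the null hypothesis with Type I error probability of 0.05".

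Two other places give the 6-minute walk some prominence. Section 3.4 says that "it offers the possibility of an inexpensive, accurate and valid tool to assess the effects of Entresto", and the second secondary objective reads "To assess the time required for functional improvements (6 minute walk test) to return to baseline".

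**The concern.** A reader of section 9.2 would naturally take 0.05 and 0.85 as the operating characteristics of the primary objective. That follows only if a single test decides the objective, and the plan does not say that one does.

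Two success rules fit the text equally well. Under one, a significant result on any of the three outcomes is enough, and the false-positive rate exceeds 0.05. Under the other, all three must be significant; error is then controlled, but power is below 0.85. Because neither is written down, the rule could be settled after the results are known. What is at stake is what the trial may claim on its primary objective.

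**Working it through.** **Inputs.** From section 9.2: effect 278 m, SD 240 m, Type I error 0.05, power 0.85, 15 per group. From section 1.2: three primary outcomes. Assumptions, because the documents are silent: two-sided testing; a common correlation r between the three outcomes of 0, 0.5, 0.8 or 0.9; and, for the power figures, the same standardized effect on each outcome.

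**Step 1: reproduce section 9.2.** d = 278 / 240 = 1.158. For a two-sided, two-sample t-test at 0.05, power 0.85 needs 14.41 per group, so 15. Exact power at 15 per group is 0.865. A one-sided t-test would need 12 per group, so the stated figure matches a two-sided test. The calculation is correct for one test of pain-free walking distance.

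**Step 2: any one of three counts, no true effect.** For independent outcomes: 1 − (1 − 0.05)^3 = 1 − 0.857 = 0.143. For correlated outcomes, the chance that at least one of three two-sided tests rejects was found by numerical integration for equicorrelated normal statistics, and by simulating t-tests with 15 per group.

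| Assumed r | False-positive rate, any of three |
|---|---|
| 0 | 14.3% |
| 0.5 | about 12.6% |
| 0.8 | about 9.8% |
| 0.9 | about 8.4% |
| 0.99 | about 6.0% |
| 1 | 5.0% |

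**Step 3: all three required.** Error cannot exceed 5%, because the objective is met falsely only if at least one outcome with no effect is itself significant at 0.05. Power with d = 1.158 on every outcome is 0.865^3 = 0.65 if they are independent, and by simulation about 0.71, 0.77 and 0.80 at r = 0.5, 0.8 and 0.9. The single-outcome figure is 0.865.

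**Step 4: the remedies at 15 per group.**
- One primary outcome: power 0.865 for it, unchanged.
- Fixed order, d = 1.158 on all three. Second outcome: 0.865^2 = 0.75 at r = 0, rising to about 0.83 at r = 0.9. Third outcome: 0.65 rising to about 0.80, the same as requiring all three.
- Holm on three primary outcomes: the smallest p value is tested at 0.05 / 3 = 0.0167. If only pain-free walking has an effect (d = 1.158), its power is about 0.73.

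**The case against.** The strongest defence is that section 9.2 speaks of one null hypothesis, for pain-free walking distance, and makes no claim about all of section 1.2. That stands: section 9.2 is not wrong in itself. But section 1.2 does not name pain-free walking as the lead outcome, so the calculation does not settle what decides the objective.

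A second defence is that this is a 30-patient, single-university study whose objective is to assess effects, and that section 9.1 judges clinical importance by effect size. This bears on how much weight the result will carry. It does not remove the gap, because section 9.2 commits to rejecting a null hypothesis at 0.05.

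Several stronger readings are tempting and should not be drawn:
- A reader might infer that the trial's error rate is 14.3%, or at least 8.4%. Both need the any-one rule, which the plan does not state, and each needs an assumed correlation. The lower figure is not a floor.
- A reader might infer that the documents favour the 6-minute walk over the pain-free walking used for sizing. Sections 2.1 and 3.4 introduce it as an additional test, and the second secondary objective concerns loss of benefit after treatment. Neither ranks the primary outcomes.
- A reader might infer that having both a t-test and a repeated measures ANCOVA adds a further, calculable error. The model is not specified well enough to say. With baseline and week 12 only and no other covariate, its group-by-time test is the same as a t-test on change. The analysis that decides should still be named.

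**Conclusion.** The concern holds in this form: the primary objective has three unranked outcomes, one unadjusted threshold and no success rule, so the plan does not show that 0.05 and 0.85 apply to it. Both figures are correct for a single test of pain-free walking distance.

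The size depends on the missing rule. If any one outcome suffices, the false-positive rate lies between 5% and 14.3% for non-negative correlation, and is about 8.4% to 12.6% at assumed correlations of 0.9 down to 0.5. If all three are needed, error is at most 5% and power is about 0.65 to 0.80 at correlations from 0 to 0.9, assuming d = 1.158 on every outcome. The documents give neither the correlations nor the effects on the other two outcomes. That no rule is stated rests on the text alone and needs no assumption. It should be fixed before unblinding.

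**What to change.** Before unblinding, write one success rule into sections 1.2 and 9.1.

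**Preferred.** Name one primary outcome and one between-group analysis. Pain-free walking, by t-test on change to week 12, matches section 9.2, provided the sections agree on the measure: sections 1.2 and 3.4 define a duration, while section 9.2 uses a distance in metres. Make the other two outcomes key secondary, tested in a stated fixed order or by Holm, and label the repeated measures ANCOVA supportive. If the sponsor prefers another outcome, such as the 6-minute walk, section 9.2 must be restated for it.

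**Alternative.** Keep all three primary and apply Holm at 0.05.

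Under either route, state in section 9.2 that 0.85 applies to pain-free walking only.

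**Cost.** Wording only, with no extra patients. Under the preferred route two outcomes lose equal-primary status. Power for the first stays at 0.865; in fixed order, if all have d = 1.158, it is about 0.75 to 0.83 for the second and 0.65 to 0.80 for the third. Under Holm on three primary outcomes, power for pain-free walking falls to about 0.73 if the other two have no effect. About 20 per group would be needed only if the sponsor wanted 0.85 in that case.
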